#### Data Analysis

Complex survey design: The MCBS uses a multi-stage clustering sample with unequal sampling probabilities. We will take into account the complex design by using appropriate survey commands in Stata to calculate the correct point estimates and their variances. Specifically, the set of longitudinal weights (RIC X2) allowing analysis of data trends over a two year period and a second set of longitudinal weights (RIC X3) will be applied to two- and three-year outcomes.

Proxies: Proxy responses will be included in all models. About 9.8% of MCBS baseline interviews were conducted by proxies and our previous work indicates that exclusion of proxy responses results in underestimates of disability prevalence. Recognizing this may explain proxy differences we will explore replacing proxy status with reason for proxy use.

Missing data and attrition: See Avoidance of Bias below.

General approach to analysis: Each Aim will describe the sample of Medicare beneficiaries with weighted uni-variable summary statistics appropriate to the distributional characteristics of the variables of interest and bi-variable associations with outcomes. Because of concerns that some variables may be intermediate on causal pathways, to understand associations, we will build etiological models hierarchically. All will control for baseline age, gender, race, ADL or

PRINCIPAL INVESTIGATOR (LAST, FIRST, MIDDLE): [name]

IADL stage, and proxy status. Health conditions and living circumstances will be added sequentially, selected according to associations with functional change, institutionalization, or mortality or according to emergent themes from stakeholder groups. The Goodness-of-Fit (GOF), Deviance and Pearson GOF Statistic, ROC curve, and r-square values as appropriate to each regression will be reported to document model fit of the multinomial regressions. Stata 11.0 (Stata Corp, College Station, Texas) will be used for all analyses (except for multiple imputation as noted below). A 2-sided  $p<.05$  will be used for all final tests of significance.

**Aim 2** will address the degree to which people with disabilities experience healthcare disparities. The comparators will be the outcome here and ADL/IADL stages will be the main exposure. We will model each trichotomously expressed comparator through multinomial logistic regression. We will report adjusted relative risk ratios (RRRs) and their 95% confidence intervals (CIs) for the ADL and IADL stages (stage I as reference). For each continuously expressed comparator, we will report sample weighted estimates for the ADL and IADL stages (stage I as reference) obtained through linear regression.

**Aim 3** will determine if people who experience better access and higher quality healthcare and who rate their PCPs highly on technical skills, inter-personal manner, and the provision of sufficient information to understand their health condition(s) will be less likely to experience a negative transition outcome. The 5-state transition outcome will be modeled by multinomial logistic regression models with no change in function as reference. We will report RRRs and their 95% CIs. In the multinomial logistic regression, the relative risk of improvement in function, decline in function, institutionalization, or death will be defined as the probability of improvement in function, decline in function, institutionalization, or death divided by the probability of remaining at the same ADL stage.

Each of the 5 comparators will be modeled individually after considering other covariates. They will also be entered into one model to determine the relative independent effects of each after considering the other exposures.

**Aim 4** While models for aims 2 and 3 will be etiological and explanatory, the policy simulations will be predictive. We will simulate the maximum benefit of healthcare programs or policies aimed at improving each comparator, i.e., coordination and quality of care, increasing access, PCP technical skills, PCP interpersonal skills, and the quality of information provided by PCPs on likelihood of functional improvement, functional decline, institutionalization, or death over 1, 2, and 3 years. Taking the scenario of increased access as example, the simulation will: estimate the effect of poor access to care according to the transition outcome using  $\beta$ -coefficients from a multinomial regression similar to those proposed in Aims 2 and 3, i.e., we will use coefficients to predict status according to the multiple outcome states of "improved in function," "deteriorated in function," "institutionalized," and "died" by 1-, 2- and 3-year follow-up compared to "remained at the same ADL stage," given the new optimized access comparator, while holding baseline ADL stage and all other variables constant at the individual-levels. This will allow creation of new population prevalence estimates for each of the outcome states assuming optimal access. Comparison of these predicted/adjusted values and their associated confidence intervals will show the relative potential of policies targeted to improve the access comparator (when compared to any other policy change scenario) included in the simulation. Simulations will be performed for the 1-, 2- and 3-year time frames and for ADL and IADL stage transitions. This will produce a table showing the regression-based, predicted effects of optimizing alternative comparators on population status. These simulations will help frame the results of our study according to the "comparative effectiveness" of alternative policy instruments targeted to the 5 quality comparators. These findings will be triangulated with thematic materials extracted from the stakeholder groups (see above).

PRINCIPAL INVESTIGATOR (LAST, FIRST, MIDDLE): [name]

The **Patient-Informed Surveillance Tool** will be developed in three steps using an approach we applied recently. (1) assess the quality of candidate predictors through the combined input of stakeholder and researcher recommendations with demonstrated bi-variable associations  $p < .20$ ; (2) beginning with a regression containing all candidate covariates, estimate a parsimonious model by using backward selection to remove all candidate variables at  $p > .05$ ; (3) develop a simply applied point-scoring system from the estimates associated with each variable in the final model by dividing each significant  $\beta$ -coefficient by the lowest significant  $\beta$ -coefficient and rounding to the nearest integer. A value of "0" will be assigned to non-significant  $\beta$ -coefficients. Depending on demonstrated affect modification, working-aged and elderly beneficiaries might be included in separate Tools. The final set of **Patient-Informed Surveillance Tools** will group sub-populations by outcome expectation as determined by perceptions according to each comparator adjusted for ADL or IADL stage, living circumstances (i.e., family members who might provide care, home accessibility, etc.), diagnoses, socioeconomic status (i.e., income, education, etc.), comparator status, and other covariates. The final selection of variables in the Tools will be informed by stakeholder input (see above) as well as statistical findings.

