Activity Limitation Stages determined during the baseline fall interview will be the key independent variable (see Table 1 for definitions). ADL stages (0-IV) will be primary and IADL stages (0-IV) analyzed secondarily. IADLs such as meal preparation are not always relevant when someone else is available to perform those tasks, yet IADL enables exploration of the effects of milder disabilities.

Other covariates: *Working age* 21 to 64 and 65 and over; *gender*; *race* (African American or Black, Hispanic, White, and other); *education* (high school graduation Y/N); *marital status* (married/unmarried); *income* (Medicare categories of annual household income from all sources); *insurance type* (Medicare only, Medicare and Medicaid-dual enrollee, private-supplemental, other (i.e., Champus, VA)); *living arrangement* (i.e., lives alone or with spouse only, with children, with other relatives or non-relatives, or in a retirement community); and the *presence or absence of accessibility features in the home* (home accessibility features). Health status will be captured by physician-reported *chronic conditions and impairments* (hypertension, asthma, diabetes, COPD, coronary artery disease, and congestive heart failure, intellectual and/or developmental disability, dementia or Alzheimer’s disease, neurological disorders, mental illness, no usable vision, and deaf). Building on our previous work, we know that the nature and severity of disabilities resulting from these conditions can be expected to vary. As example, neuropsychiatric conditions, particularly those causing intellectual disabilities, are often extremely disabling, while people who are blind or deaf often find ways to accommodate and perform basic activities. Analyses will control for residence based on Census regions.

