Dissatisfied vs. neither dissatisfied nor satisfied	1.71	2.71	1.50	1.49
Satisfied vs. neither dissatisfied nor satisfied	1.24	1.63	1.16	0.90

Qualitative: The SL group analyses will include geographically diverse stakeholders with a variety of socioeconomic circumstances, disabilities, comorbidities, and life circumstances. The SL groups will be computer literate. The addition of Urban groups further enriches the sample

PRINCIPAL INVESTIGATOR (LAST, FIRST, MIDDLE): [name]

by obtaining PWD from a predominantly minority low literacy population. The SL and Urban recruitment strategies enable the inclusion of hard-to-reach people, including those who face numerous disability-related, economic, educational, social class, ethnicity, and cultural barriers.

By design, the MCBS samples are weighted to be representative of the entire elderly and working age Medicare population, and thus by its nature will include a diverse study population. The sample will also have a wide range of medical comorbidities. Preliminary results (Table 5) show diversity with respect to ADL and IADL stage as well as transition outcome status (above). Finally, the sampling frame is designed to be geographically diverse. Table 5 provides sample size estimates from 3 active panels of respondents at the fall 2006 Access to Care interview (about 3/10ths the study sample size). Over 4 and 5 million people had mild ADL or IADL limitations, respectively, with another 4.6 and 7.0 million people having more serious ADL and IADL limitations. Between-group differences across the 5 comparators will be addressed quantitatively according to the transition outcomes with independent effects of ADL and IADL stage determined.

Table 5. Sample size shown for 3 panels; expected size for 10 panels will be 40,000

Stage	Difficulties in ADL			Difficulties in IADL		
	Raw N	Expected N in population (million)	Weighted percent (SE on weighted %)	Raw N	Expected n in population (million)	Weighted percent (SE on weighted %)
0	8208	21.1	69.25 (0.86)	6924	18.2	59.65 (0.97)
I	1942	4.8	15.73 (0.50)	2094	5.3	17.5 (0.59)
II	995	2.4	7.72 (0.37)	1141	2.9	9.45 (0.37)
II	728	1.8	5.97 (0.36)	1558	3.4	11.1 (0.41)
IV	185	0.4	1.33 (0.14)	341	0.7	2.3 (0.15)
Total	12058	30.5	100	12058	30.5	100

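### The Aim 3 transition models, and the Aim 4 simulations built on them, adjust for only one baseline stage (ADL or IADL) although both are measured; both should be covariates.

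*Combined protocol and SAP*

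**What the plan says.** Under Data Analysis (General approach to analysis), the etiological models are built hierarchically. The core set is "All will control for baseline age, gender, race, ADL or" "IADL stage, and proxy status"; a page header splits the sentence. Health conditions and living circumstances come later: they "will be added sequentially, selected according to associations with functional change, institutionalization, or mortality", or are chosen from stakeholder themes. The second functional stage belongs to neither group, and it is not in the list of other covariates.

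The paragraph on Activity Limitation Stages says that "ADL stages (0-IV) will be primary and IADL stages (0-IV) analyzed secondarily". It gives a reason: "IADLs such as meal preparation are not always relevant when someone else is available to perform those tasks". It adds that IADL is useful for exploring milder disability.

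Aim 4 sets a comparator to its best level and predicts outcomes "while holding baseline ADL stage and all other variables constant at the individual-levels". It also states: "Simulations will be performed for the 1-, 2- and 3-year time frames and for ADL and IADL stage transitions". The Surveillance Tool text again names one stage or the other.

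The text before Table 5 in the Sample size section says that comparator differences will be examined against the transition outcomes "with independent effects of ADL and IADL stage determined".

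**The concern.** Aim 3 estimates how perceived access and quality relate to later improvement, deterioration, institutionalization and death. Baseline function is a leading candidate confounder, and the plan treats it that way. Aim 2 makes ADL and IADL stage the main exposure for the same comparators, and the Year 2 deliverables in Table 9 include the independent effect of initial stage on transitions.

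If only ADL stage is in the primary models, two people with no ADL difficulty count as functionally equal at baseline even when one has IADL limitations. If the two also tend to differ in perceived care and in prognosis, part of that difference is credited to the comparator. Aim 4 then turns the coefficients into maximum-benefit estimates that compare policies, so any such bias would pass into the comparison.

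The Avoidance of bias section relies on a content-rich data source to limit confounding. Leaving out a functional variable that the source measures works against that argument.

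**Working it through.** **Inputs.** Table 5 (three panels, fall 2006), stages 0 to IV. The second row labelled II is read as stage III.
- ADL raw N: 8,208; 1,942; 995; 728; 185. Weighted %: 69.25; 15.73; 7.72; 5.97; 1.33.
- IADL raw N: 6,924; 2,094; 1,141; 1,558; 341. Weighted %: 59.65; 17.5; 9.45; 11.1; 2.3.

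**Reproducing the table.** Both raw columns sum to 12,058 and both weighted columns to 100. Scaling to ten panels, 12,058 × 10/3 = 40,193, which agrees with the stated 40,000. The table is internally consistent. It gives no ADL-by-IADL cross-tabulation, so only bounds on the overlap can be derived.

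**Share of ADL stage 0 with any IADL difficulty.** Minimum = (ADL0 − IADL0)/ADL0. Maximum = min(ADL0, total − IADL0)/ADL0.
- Raw minimum: (8,208 − 6,924)/8,208 = 1,284/8,208 = 15.6%.
- Weighted minimum: (69.25 − 59.65)/69.25 = 9.60/69.25 = 13.9%.
- Raw maximum: (12,058 − 6,924)/8,208 = 5,134/8,208 = 62.5%.
- Weighted maximum: 40.35/69.25 = 58.3%.

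The weighted floor is the relevant one, because the analyses are survey-weighted. It is itself an estimate. If the two percentages are treated as independent, the SE of their difference is √(0.86² + 0.97²) = 1.30. Then 9.60 ± 1.96 × 1.30 is 7.06 to 12.14, or 10.2% to 17.5% of ADL stage 0 (denominator held fixed).

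**How severe the guaranteed overlap is.** Under Table 1, IADL stage I requires no difficulty with telephone, money, meals or light housework, which leaves shopping and heavy housework. The guaranteed number at ADL stage 0 with IADL stage II or worse is max(0, 8,208 − (6,924 + 2,094)) = max(0, −810) = 0. All 1,284 could be IADL-I.

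**Mismatch at the severe end.** The minimum number at IADL III-IV who are not at ADL III-IV is the difference between the two totals.
- Raw: (1,558 + 341) − (728 + 185) = 1,899 − 913 = 986; 986/1,899 = 52%.
- Weighted: (11.1 + 2.3) − (5.97 + 1.33) = 13.4 − 7.3 = 6.1; 6.1/13.4 = 45.5%.

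These people are at ADL 0, I or II. The margins do not say which.

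**The reverse direction.** The guaranteed number at IADL stage 0 with ADL difficulty is max(0, 6,924 − 8,208) = 0. Table 5 therefore gives no numerical floor for the IADL-transition models.

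**Whether a bias can be sized.** For one omitted binary factor, the bias factor is [1 + p1(RR − 1)]/[1 + p0(RR − 1)]. Here p1 and p0 are its prevalence in the dissatisfied and middle groups, and RR is its effect on the outcome. The documents give none of these conditional on ADL stage and the other covariates. Assumed values show how far the answer depends on them:
- p0 = 15%, p1 = 16%, RR = 1.5: 1.080/1.075 = 1.005.
- p0 = 15%, p1 = 20%, RR = 3: 1.40/1.30 = 1.08.
- p0 = 15%, p1 = 25%, RR = 5: 2.00/1.60 = 1.25.

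If p1 were below p0, the factor would fall below 1.

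**The case against.** The strongest reply is that the word or has an ordinary meaning here: each model carries the stage that matches its outcome. The plan gives a reason for ranking IADL second and builds its models hierarchically because some variables may be causal intermediates. Proxy status is forced in, and dementia, intellectual disability, mental illness, neurological disorders, living arrangement and home accessibility are all candidates for later steps. Much of what IADL stage would add may already be covered.

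Part of this stands. Matching stage to outcome is a plausible reading, and the other covariates would absorb some of the difference. But matching still leaves IADL stage out of the primary ADL models. The reason for ranking IADL second concerns its role as an exposure and does not argue against it as a covariate. A worry about intermediates applies equally to baseline ADL stage, which is already forced in. The health and living covariates enter only after selection, and none of them is a measure of function.

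A reader might infer from the Sample size wording that a joint model is already required. The text does not settle this. Independent effects can mean effects adjusted for covariates, and Table 9 uses similar language for initial stage alone. The wording conflicts with the covariate list or is ambiguous; either way it needs clarifying.

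**Conclusion.** The point holds as a gap in confounding control. Each Aim 3 model carries one baseline stage, Aim 4 follows, and no joint model or sensitivity analysis is specified. At least 13.9% weighted (15.6% raw) of ADL stage 0 has some IADL difficulty, and at least 45.5% weighted (52% raw) of IADL III-IV sits at ADL 0-II. These bounds assume that the 2006 three-panel margins resemble the full sample, as the plan's own power calculation does.

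Three stronger readings are tempting and not supported:
- **That the ADL stage 0 floor is 16%.** That rounds the raw figure up, and the weighted floor is lower.
- **That people at ADL stage 0 are shown to have difficulty with money, telephone or meals.** The guaranteed number is zero.
- **That the comparator effects are confounded by a known amount.** Factors from 1.005 to 1.25 follow from different assumed inputs, and the direction is also open. Confounding is plausible but unquantified.

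For the IADL-transition models, the case rests on the same reasoning and not on Table 5. The change is worth making because it is cheap and uses data already in hand. The documents do not show that the planned results would be wrong without it.

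**What to change.** In the general analysis approach, replace the single stage in the forced covariate set with baseline ADL stage and baseline IADL stage, each at five levels, for the Aim 3 and Aim 4 transition models. Keep ADL transitions primary and IADL transitions secondary. In Aim 4, state that both baseline stages are held at their individual values. In the Sample size section, say whether independent effects means effects from this joint model.

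No new data are needed. The cost is four coefficients per outcome equation. With four non-reference outcomes that is 4 × 4 = 16 per model, on about 40,000 people. The two stages are likely to be correlated, so their own coefficients will be less precise. That matters less for the comparator coefficients, which are the target. The sparsest level is ADL stage IV, with 185 people in three panels (about 185 × 10/3 = 617 in ten), so the joint ADL-by-IADL table should be inspected before the models are fitted. Reporting the single-stage model alongside would show how far the comparator estimates move.

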**Quantitative: Overview and General Approach to Multivariable Estimation:** Our specific aims focus on empirically quantifying disparities in the quality of health and PCP care as perceived by PWD compared to PWOD and the impact of any disparities identified on transition outcomes. Taking advantage of the large nationally representative contemporary cohort of Medicare beneficiaries enrolled over a decade in the MCBS, quantitative methods will begin by

PRINCIPAL INVESTIGATOR (LAST, FIRST, MIDDLE): [name]

exploring the associations of all covariates to ADL and IADL stage transitions over 1, 2- and 3-year periods. A series of multivariable regressions will be implemented in Aims 2, 3, and 4 to provide a comprehensive perspective on disparities and the factors influencing transitions. After quantifying the net contribution (if any) of each comparator to outcome transitions, we will then use parameter estimates generated by these analyses in the Aim 4 simulation study. The goal will be to simulate the maximum effect of alternative programs intended to improve access to care, quality of care, and the technical and other qualities of PCPs on the wellbeing of the US Medicare population.

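### For Aim 2, covariates are picked by their association with later transitions, not with the care ratings being modelled, and no Aim 2 adjustment set is named

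*Combined protocol and SAP*

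**What the plan says.** Under Data Analysis, the general-approach paragraph sets one scheme for the etiological models, built hierarchically because some variables may lie on the causal path.

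- **Fixed core.** "All will control for baseline age, gender, race, ADL or" IADL stage, plus proxy status. The covariate paragraph adds region: "Analyses will control for residence based on Census regions".
- **Selected variables.** Health conditions and living circumstances "will be added sequentially, selected according to associations with functional change, institutionalization, or mortality". The same sentence gives a second route: "or according to emergent themes from stakeholder groups".
- **Scope.** The Aim 4 paragraph brings Aim 2 under the scheme: "While models for aims 2 and 3 will be etiological and explanatory".
- **Aim 2 model.** "The comparators will be the outcome here and ADL/IADL stages will be the main exposure". For reporting: "We will report adjusted relative risk ratios (RRRs) and their 95% confidence intervals (CIs) for the ADL and IADL stages". The variables behind the adjustment are not listed.
- **Project plan.** The quantitative overview starts by "exploring the associations of all covariates to ADL and IADL stage transitions over 1, 2- and 3-year periods". It describes no parallel step for the care ratings.

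The covariate paragraph also lists education, marital status, income, insurance type, living arrangement, home accessibility features and chronic conditions. It does not say which of these enter the Aim 2 models.

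**The concern.** A confounder of the stage-rating relation is related to stage and to the rating. The association criterion asks instead whether a variable is related to functional change, institutionalization or death. Those are outcomes of Aims 3 and 4, so the criterion suits Aim 3 but does not address Aim 2.

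At stake are the adjusted RRRs for stage, which are the plan's evidence on whether disability-related disparities in care exist. If a relevant variable is missing, those RRRs can be pushed in either direction, and a larger sample does not cure that. Because the Aim 2 set is unnamed, two analysts could also follow the plan faithfully and report different disparity estimates.

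**Working it through.** **1. Rule against model.**

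| | Exposure | Outcome | Association criterion looks at |
|---|---|---|---|
| Aim 2 | ADL/IADL stage | five care ratings | transitions |
| Aim 3 | care ratings | transitions | transitions |

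The criterion matches the outcome in Aim 3 only. No section gives a criterion based on ratings, or on stage and ratings together. Each Aim will describe bivariable relations with its own outcomes, but the plan does not make that description a selection rule.

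**2. What would have to happen for a variable to be lost.** A condition or living circumstance enters if it is associated with any one of the three transition endpoints, or if stakeholders raise it. To be lost, it must be related to stage and ratings, unrelated to all three endpoints and not raised by stakeholders. It must also confound beyond age, gender, race, proxy status and region. The documents identify no such variable and exclude none.

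**3. Education, income and insurance.** These are not in the fixed core. The rule covers health conditions and living circumstances, and the Patient-Informed Surveillance Tool paragraph lists socioeconomic status (income, education) separately from living circumstances. The gap here is silence about where they enter, not removal by the rule. They matter because the Background reports lower income and education among people with disabilities, and the access comparator includes out-of-pocket cost.

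**4. Possible size.** The documents give no figure for this, so all inputs are assumed. For one omitted binary factor with prevalence p1 and p0 in the two stages and ratio G with dissatisfaction, the approximate multiplier on the stage contrast is

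[1 + p1(G − 1)] / [1 + p0(G − 1)].

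With p1 = 0.30 (stage III) and p0 = 0.15 (stage I):

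- G = 0.7: 0.910 / 0.955 = 0.953
- G = 1.5: 1.150 / 1.075 = 1.070
- G = 2.0: 1.300 / 1.150 = 1.130

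Over a wider grid, the multiplier runs from 1.0375 / 1.025 = 1.012 (G = 1.25, 15% vs 10%) to 1.80 / 1.40 = 1.286 (G = 3, 40% vs 20%).

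**5. Scale against Table 3.** Table 3 concerns power and is used here only as a yardstick. As a rough check of it, Table 5's raw shares of 40,000 give 8,208/12,058 × 40,000 = 27,228 people at stage 0 and 1,942/12,058 × 40,000 = 6,442 at stage I. A two-proportion calculation at 80% power and 5% significance, with reference shares 13.32% and 26.49%, gives 0.904 and 1.065, against the stated 0.91 and 1.07. Restricted to the two categories compared, it gives 0.888 and 1.094.

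- *Stage III vs I* (stated 1.16 and 0.88): the example's 0.953 to 1.130 stays inside these values. A stronger factor does not: G = 2 with 40% vs 20% gives 1.40 / 1.20 = 1.167.
- *Stage 0 vs I* (stated 0.91 and 1.07): a factor commoner at stage I acts as the reciprocal. G = 2 with 25% vs 15% gives 1.15 / 1.25 = 0.92, just short of 0.91. With 30% vs 15% it gives 1.15 / 1.30 = 0.885, which passes it.

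A weak factor is therefore negligible. A moderate one is comparable with the smaller contrasts the plan hopes to detect.

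**The case against.** The strongest reply has four parts.

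- **The rule has two routes.** Aim 1 themes concern the five comparators, so the stakeholder route may bring in determinants of ratings. This stands, and it narrows the gap. But themes from purposively sampled focus groups are not a systematic check for confounding and guarantee no variable.
- **Much is already adjusted.** The core demographics, proxy status and region are in every model. The human-subjects section says socioeconomic data are needed to adjust outcomes, so intent to adjust is on record. This stands too. What is missing is where those variables enter Aim 2.
- **No lost confounder has been named.** That is correct. Many predictors of decline or institutionalization will also predict ratings and so will enter anyway.
- **More adjustment is not always better.** Income, insurance and home features may be consequences of disability, and adjusting for them could remove part of the disparity Aim 2 is meant to measure. This stands, and it rules out simply forcing the complete list into one final model.

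The plan also foresees a later protocol with analysis plans and variable specifications. That is a convenient place for the correction, but it does not supply one.

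**Conclusion.** The concern holds in a limited form. For Aim 2 the stated association criterion targets the wrong outcomes, nothing replaces it, and the adjustment set is not named. This is a mis-aimed rule as well as missing detail.

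A reader might infer that the Aim 2 RRRs will be confounded, or that all covariates are chosen by transition outcomes. The documents support neither. Selection applies only to health conditions and living circumstances, a second route exists, and omission is possible but not established.

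The size rests entirely on assumed prevalences and ratios: about 0.95 to 1.13 on the stage RRR in the stage III example, and about 1.01 to 1.29 over the wider grid of harmful factors. The formula is approximate and treats one binary factor, without effect modification and not already accounted for by the fixed core.

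**What to change.** For Aim 2 only, replace the transition-based criterion with an adjustment set named in advance. Draw it from the covariates already listed and choose it by relation to stage and to the comparators. Stakeholder themes can still add variables, with the addition documented.

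Keep the hierarchical build and make the steps explicit:

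1. the fixed core and region;
2. education, income and insurance, as a named step;
3. living circumstances, including home features;
4. health conditions and impairments.

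Report the stage RRR and its interval at each step, so that estimates before and after possible mediators are both visible. State that the fully adjusted model is not the sole disparity estimate.

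The cost is a change of wording and somewhat more analysis and reporting. No new data are needed, because every variable is already in the plan's list. The Aim 3 rule can stay as it is for this purpose.
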